8.4 Reporting of Serious Adverse Events

All SAEs must be reported, whether or not considered causally related to the investigational product, or to the study procedure(s). All SAEs will be recorded in the eCRF.

Should an SAE occurs during the course of the study, Investigators or other site personnel must inform Aegerion or designee per Section 8.6 within 1 day, i.e., immediately but **no later than 24 hours** of when he or she becomes aware of it.

The designated Aegerion representative or designee will work with the Investigator to ensure that all the necessary information is provided to the Aegerion Patient Safety data entry site **in a timely manner** for fatal and life-threatening events of initial receipt for all other SAEs

For all SAEs, including fatal or life-threatening, where important or relevant information is missing, active follow-up is undertaken immediately. Investigators or other site personnel inform Aegerion representatives or designee of any follow-up information on a previously reported SAE within 1 calendar day, i.e., immediately but **no later than 24 hours** of when he or she becomes aware of it.

8.5 Overdose

An overdose is considered a dose of metreleptin that exceeds the maximum dose of 10 mg/day for patients >40 kg (refer to the US prescribing information) and should be recorded on the AE CRF when an AE is associated with the overdose. If no AE is associated with the overdose, the event should be recorded on the Overdose CRF.

• An overdose with associated SAEs is recorded as the SAE diagnosis/symptoms on the relevant SAE modules in the eCRF and on the Overdose eCRF module.

Confidential Page 41 of 58

If an overdose on an Aegerion study drug occurs in the course of the study, then the Investigator or other site personnel inform appropriate Aegerion representatives or designee immediately, or **no later than 24 hours** of when he or she becomes aware of it.

The designated Aegerion representative or designee works with the Investigator to ensure that all relevant information is provided to the Aegerion Patient Safety data entry site.

For overdoses associated with an SAE, the standard reporting timelines apply, see Section8.4. For other overdoses, reporting must occur within 30 days.

8.6 Reporting Adverse Events

The principal investigator or site personnel are responsible for detecting, documenting, and reporting all events that meet the definition of an AE or SAE.

All SAEs and unanticipated events, occurring after the signing of the ICF up until either the scheduled Follow-up Visit or at least 4 weeks after the last dose of study medication in the case of an early termination, and regardless of study medication relationship, must be reported via email or by fax to Aegerion or designee within 24 hours of investigator awareness of the event on the SAE/AESI form.

Serious Adverse Event Contact Information:

Email: [contact]

Facsimile: US [contact]

Facsimile: Rest of World [contact]

This form will capture data surrounding the event, e.g., the nature of the symptom(s), time of onset in relation to initiation of therapy, duration, intensity, and whether or not therapy was interrupted or discontinued. The principal investigator's assessment of causal assessment of the event to metreleptin exposure will also be included. In addition, relevant medical history, concomitant medications, laboratory and diagnostic tests reports, and procedures as well as all pertinent medical information related to the event will be collected.

Confidential Page 42 of 58

Should there be incomplete or missing information, Aegerion or designee will forward SAE queries directly to the investigator requesting additional information. It is the investigator's responsibility to be diligent in providing this information to Aegerion or designee as soon as it is available. Initial reports of SAEs should never be left on telephone voicemails.

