2.2 Rationale for Study Design, Doses and Control Groups

This study is being conducted to satisfy a postmarketing requirement to assess the immunogenicity associated with metreleptin treatment. Because immunogenicity can only be evaluated in the context of drug treatment, the study is open-label and will characterize antibody and *in vitro* neutralizing activity over time and will compare safety and tolerability in patients with different antibody statuses (e.g., binding antibody titer, *in vitro* neutralizing activity category, in vitro neutralizing activity percent inhibition). Immunogenicity will be evaluated in the context of the prescribing information for MYALEPT; thus, the patient population and dosing will be per the US prescribing information (MYALEPT Prescribing Information).

Anti-metreleptin and anti-HuL binding antibody titers over time will be evaluated in order to establish a time course of antibody development and to assess the development of antibodies that recognize the endogenous protein. Because samples from a few patients treated with metreleptin have demonstrated *in vitro* neutralizing activity in an *in vitro* cell-based assay, *in vitro* neutralizing activity will also be assessed in all antibody positive samples. To provide an orthogonal method to evaluate potential *in vitro* neutralizing activity, all antibody positive samples will also be assessed using a ligand-binding assay.

Safety and tolerability of metreleptin associated with the development of, or absence of, antibodies will be evaluated. All adverse events (AEs) will be collected throughout the course of this study. Serious adverse events (SAEs), adverse events of special interest

Confidential Page 17 of 60

(AESI) AEs leading to discontinuation, standard laboratory tests and vital signs will be collected over time and analyzed for any potential association with antibody status. See Section 8.2 for definitions of AEs and AESIs

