4.11.1 Procedures for Discontinuation of a Patient from Metreleptin

At any time, patients are free to discontinue metreleptin, without prejudice to further treatment. When discontinuing metreleptin in patients with risk factors for pancreatitis (e.g., history of pancreatitis, severe hypertriglyceridemia), tapering of the dose over a 1-week period is recommended. During tapering, triglyceride levels should be monitored and initiation of or adjustment of the dose of lipid-lowering medications should be considered, as needed. Signs and/or symptoms consistent with pancreatitis should prompt an appropriate clinical evaluation.

A patient who decides to discontinue metreleptin will be asked about the reason(s) and to specify any AEs or SAEs leading to discontinuation. If possible, patients should be seen and assessed by the Investigator(s). Adverse events will be followed up (see Section 8). Patients should return for all protocol-specified visits to allow for continued assessments, even if metreleptin has been discontinued. In addition to AESIs (refer to Section 8.3.8) and SAEs, samples for antibodies and *in vitro* neutralizing activity should be collected after discontinuation of metreleptin.

Patients who discontinue metreleptin may restart treatment at any time during the 3-year study period.

If a patient is withdrawn from the study, see Section 4.12.

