8. SAFETY REPORTING AND MEDICAL MANAGEMENT

The Principal Investigator is responsible for ensuring that all staff involved in the study is familiar with the content of this section.

All adverse events, including SAEs, adverse events leading to discontinuation, and AESIs will be recorded on the eCRF. Additionally, all SAE and AESI that require immediate reporting will be captured on the SAE/AESI form and sent to the pharmacovigilance department (see Section 8.6).

Confidential Page 36 of 58

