8.3 Recording of Adverse Events

8.3.1 Time Period for Collection of Adverse Events

Adverse events (AE), including serious adverse events (SAE), AEs leading to discontinuation and AESIs will be recorded from the signing of the informed consent or if the AE or AESI is related to study procedure.

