8.3.5 Adverse Events Based on Signs and Symptoms

All adverse events, including SAEs, AEs leading to discontinuation, or AESIs spontaneously reported by the patient or care provider, or are reported in response to the open question from the study personnel or revealed by observation will be collected and recorded in the eCRF. When collecting AEs, the recording of diagnoses is preferred (when possible) over recording a list of signs and symptoms. However, if a diagnosis is known and there are other signs or symptoms that are not generally part of the diagnosis, the diagnosis and each sign or symptom will be recorded separately.

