#### 17.1 Adverse Events

Adverse Events (AEs) will be coded using the latest version of MedDRA, and summarized by SOC, preferred name, and intensity. Intensity is captured in the CRF. See **Section 8.1** Statistical Tests and Confidence Intervals for a description of summaries to be reported.

Adverse Events of Special Interest (AESIs) are defined as:

- The presence of Category D or E *in vitro* cell-based NAb activity (or the relevant corresponding test result from the ligand-binding method) to metreleptin
- Necrotizing pancreatitis
- Hepatic adverse events including potential drug induced liver injury (DILI)
- Severe hypoglycemia
- Severe hypersensitivity reactions
- New diagnoses of autoimmune disorders (for instance, autoimmune hepatitis, glomerulonephritis, lupus erythematosus, antiphospholipid antibody syndrome, rheumatoid arthritis)
- Autoimmune disease exacerbation
- Serious infection resulting in hospitalization
- All cancers (excluding non-melanoma skin cancer) by cancer type
- Exposed pregnancies and pregnancy outcomes.

TEAEs are defined as AEs that started or worsened in severity on or after the first dose of study medication. If it is unclear whether or not an AE is a TEAE due to partial dates, the worst case will be assumed (i.e., TEAE). See **Appendix 1** for handling of partial dates.

AEs, serious AEs (SAEs), AEs of special interest (AESIs), TEAEs, AEs possibly caused by metreleptin, and AEs leading to metreleptin discontinuation will be summarized by ADA positivity and titer, cell-based NAb positivity and titer, and RB positivity, titer, and quintile of percent

Document: Statistical Analysis Plan: AEGR-734-401: A 36-Month, Multicenter, Open Label Phase 4 Study to Evaluate the

Immunogenicity of Daily SC Metreleptin Treatment in Patients with Generalized Lipodystrophy

Author: [name], [name], [name], [name] Version Number: 2.1

inhibition. For each patient, only one event of each type will be selected to include in summary outputs. If a patient has multiple events the same type, the event with the highest severity level is selected. For patients with multiple events of the same type and severity, the event corresponding to the highest titer or percent inhibition level is selected. The corresponding titer and percent inhibition level are defined by the most recent measurement occurring prior to the event start date.

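### The protocol's rules on adverse event collection conflict, most visibly after metreleptin is stopped, while the SAP's antibody-stratified tables assume complete ascertainment to the end of follow-up

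*Protocol*

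**What the plan says.** **All events.** Protocol Section 2.2 states: "All adverse events (AEs) will be collected throughout the course of this study". Section 8 agrees: "All adverse events, including SAEs, adverse events leading to discontinuation, and AESIs will be recorded on the eCRF". Section 8.3.5 has sites record "All adverse events, including SAEs, AEs leading to discontinuation, or AESIs spontaneously reported by the patient or care provider", along with those elicited by questioning or observed. Table 1 marks the adverse event row as continuously monitored, and its last column is Visit 12 (Month 36).

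**After stopping drug.** Sections 4.11 and 4.11.1 want patients who stop metreleptin to keep attending visits for the full three years. On what is gathered in that time, Section 4.11.1 says "In addition to AESIs (refer to Section 8.3.8) and SAEs, samples for antibodies and" neutralizing activity are to be taken. Other adverse events are not named in that sentence.

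**At visits.** Sections 6.2.2 and 6.3 list only SAEs and AESIs for review, for every patient.

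**Period.** Under Section 8.3.1 events "will be recorded from the signing of the informed consent or if the AE or AESI is related to study procedure". That gives a start, an incomplete closing clause and no end. Section 8.4 requires any SAE arising in the study to be reported within 24 hours and sends the site to Section 8.6. There, reporting of SAEs and unanticipated events runs to "either the scheduled Follow-up Visit or at least 4 weeks after the last dose of study medication in the case of an early termination".

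**Analysis.** SAP Section 17.1: "TEAEs are defined as AEs that started or worsened in severity on or after the first dose of study medication". The SAP change note of 16Dec2024 bases the adverse event tables by antibody, neutralizing and receptor-blocking status on these treatment-emergent events (TEAEs). No off-drug limit appears in the text shown.

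**The concern.** In this study, stopping drug and leaving the study are meant to be different things. A patient may be off metreleptin for most of the three years and still contribute visits, antibody samples and events. The end of event collection therefore has to be tied to study participation, and the set of events collected has to be the same on and off drug. The protocol can be read more than one way on both.

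The safety objective relates events to the presence or absence of antibodies and neutralizing activity, and Section 6.4 foresees that some patients with neutralizing activity may be taken off drug. If sites read the sections differently, the antibody-stratified tables would combine time in which all events were recorded with time in which only SAEs and AESIs were, and nothing in the output would show it.

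**Working it through.** The plan states no figure to reproduce. The check is a comparison of the text, followed by a short illustration.

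**1. The rules side by side**

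| Place | Which events | Until when |
|---|---|---|
| Protocol 2.2, 8, 8.3.5, Table 1 | All | Throughout the study (2.2); Table 1 ends at Visit 12 |
| Protocol 4.11.1 (after stopping) | SAEs and AESIs named | No end given |
| Protocol 6.2.2, 6.3 (visit lists) | SAEs and AESIs | Each visit |
| Protocol 8.3.1 | All, including SAEs and AESIs | No end given |
| Protocol 8.4 | SAEs | During the study |
| Protocol 8.6 | SAEs and unanticipated events | A Follow-up Visit not in Table 1, or at least 4 weeks after last dose for an undefined early termination |
| SAP 17.1 and 16Dec2024 note | All TEAEs | No upper limit |

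None of the protocol rows resolves its difference from the others.

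**2. Which events are exposed.** SAEs and AESIs appear under every reading of 4.11.1 and 6.3. Section 8.3.8, which 4.11.1 cites, counts suspected loss of response and severe infection or sepsis as AESIs. What remains is the non-serious, non-AESI event.

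**3. Which tables use them.** Protocol Section 10.5 stratifies only SAEs, AESIs and events leading to discontinuation by antibody status. SAP Section 17.1 extends the stratified tables to all adverse events, and the 16Dec2024 note makes these TEAEs. The exposed class therefore enters through the SAP. An off-drug event is placed in a stratum by the most recent measurement before its start. For concomitant medication, by contrast, SAP Section 13 does set a limit: a start no later than 14 days after the end of study medication.

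**4. Illustration.** The stop months are assumptions; the documents give none. Scheduled day = floor(month × 30.4), from the SAP 2.1 modification history, so Month 36 = Day 1094. Off-drug days = 1094 − stop day, and share = off-drug days / 1094.

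- Month 6: 1094 − 182 = 912; 912/1094 = 83.4%
- Month 12: 1094 − 364 = 730; 730/1094 = 66.7%
- Month 24: 1094 − 729 = 365; 365/1094 = 33.4%
- Month 30: 1094 − 912 = 182; 182/1094 = 16.6%

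This is the share of one such patient's follow-up in which full recording is uncertain and the TEAE tables still count it. One patient is 1/10 = 10.0% of the planned sample in the protocol, or 1/11 = 9.1% of the number in SAP Section 4.1, and a larger share of any antibody stratum.

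**The case against.** The strongest reply is that the general rule is clear and the rest is loose drafting. Sections 2.2 and 8 and Table 1 require all events. The sentence in 4.11.1 is additive: it adds samples to SAEs and AESIs, and the same paragraph sends adverse events to Section 8. An open-ended treatment-emergent period is also defensible when drug may be restarted and the risk may outlast dosing.

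Much of this stands, and it rules out four stronger readings that a reader might infer.

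- *Events were under-recorded.* No passage shows a missed event. The documents support only a risk that depends on how sites read the sections.
- *SAE reporting stops 4 weeks after the last dose in a patient still attending visits.* The 4 weeks in 8.6 is a minimum and most naturally concerns leaving the study, and 8.4 covers any SAE in the study. Taken as a stop date, it would cover 28/912 = 3.1% of the remaining time after a Month 6 stop and 28/182 = 15.4% after a Month 30 stop, but the text does not support that reading.
- *Severe infections after stopping would be lost.* Section 8.3.8 makes them AESIs, so 4.11.1 keeps them.
- *The antibody comparison is biased toward no association.* Sections 6.2.2 and 6.3 use the narrow list for all patients, so a difference against those who stop is not established.

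The inconsistency itself is not answered. The visit lists and 4.11.1 are narrower than Section 8, collection has no stated end, and 8.6 relies on a visit that is not scheduled.

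**Conclusion.** The point holds as a conflict between sections with a limited consequence. Ascertainment of non-serious, non-AESI events may be incomplete, and it may differ between sites and between on-drug and off-drug time. The SAP's TEAE tables by antibody status nevertheless assume that it is complete. For one patient who stays to Month 36, the uncertain share of follow-up runs from 16.6% to 83.4% for stops between Month 30 and Month 6. That range rests on assumed stop times, on the patient not restarting, and on a site applying the narrow reading.

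Neither the number of patients who stopped nor the number of events affected can be derived from the documents, and no direction of bias can be claimed. The primary immunogenicity analysis does not use adverse events and is not affected.

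**What to change.** **Protocol.** Reconcile 4.11.1, 6.2.2, 6.3, 8.3.1, 8.6 and Table 1 to one rule: all adverse events, including SAEs and AESIs, from consent to Visit 12 or the last study contact, or to the existing 4 weeks after last dose if that is later. Delete or define the Follow-up Visit and early termination in 8.6.

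**SAP and study report.** The SAP change note records changes made on 26Feb2025, after database lock, so new protocol wording cannot alter what was collected. The SAP and report should therefore:

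- state which events sites actually collected after metreleptin was stopped;
- show events with onset off drug separately from those on drug;
- if only SAEs and AESIs were collected in some periods, restrict the antibody-stratified tables of non-serious, non-AESI events to the periods in which all events were collected.

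**Cost.** For the protocol rule, a few more non-serious entries, at visits that patients already attend. For the report, one extra table split and a short statement of what sites did.

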8.7 Pregnancy

Any pregnancy that occurs during study participation must be reported as an AESI via the safety monitoring system described above. If a patient becomes pregnant, they will be allowed to continue in the study; however, the decision as to whether to continue metreleptin therapy during the pregnancy will be at the discretion of the treating physician.

Information related to pregnancy will be collected using the appropriate sections of the eCRF. The pregnancy will be followed to determine the outcome. At the end of the pregnancy, information on the status of the mother and child will be collected.

8.8 Management of Metreleptin-related Toxicities

There have been reports of generalized hypersensitivity (e.g., urticaria or generalized rash) in patients taking metreleptin. If a hypersensitivity reaction occurs, patients should discuss the proper clinical treatment for the event(s), including possible discontinuation of metreleptin with the Investigator.

Dosage adjustments, including possible large reductions, of insulin or insulin secretagogue (e.g., sulfonylurea) may be necessary in some patients to minimize the risk of hypoglycemia.

Refer to the USPI for further details (MYALEPT Prescribing Information).

Confidential Page 43 of 58

9. METRELEPTIN AND OTHER TREATMENTS

9.1 Metreleptin

No study medication will be provided for this trial; patients who have been prescribed metreleptin will be included in the study and will receive the prescribed dosage of metreleptin as indicated in the USPI.

9.2 Dose and Treatment Regimens

Based on clinical response (e.g., inadequate metabolic control) or other considerations (e.g., tolerability issues, excessive weight loss [especially in pediatric patients]), the dose of metreleptin may be decreased or increased to the maximum dosage as summarized in Table 4; refer to the USPI for further details.

Table 4: MYALEPT Recommended Dosage

BASELINE WEIGHT	STARTING DAILY DOSE (INJECTION VOLUME)	DOSE ADJUSTMENTS (INJECTION VOLUME)	MAXIMUM DAILY DOSE (INJECTION VOLUME)	
Patients ≤40 kg (males and females)	0.06 mg/kg	0.02 mg/kg	0.13 mg/kg	
	(0.012 mL/kg)	(0.004 mL/kg)	(0.026 mL/kg)	
Male patients >40 kg	2.5 mg	1.25 mg (0.25 mL) to	10 mg	
	(0.5 mL)	2.5 mg (0.5 mL)	(2 mL)	
Female patients >40 kg	5 mg	1.25 mg (0.25 mL) to	10 mg	
	(1 mL)	2.5 mg (0.5 mL)	(2 mL)	

9.3 Labeling

No labels will be prepared for this study. Patients will receive commercially available metreleptin.

9.4 Storage

Metreleptin should be stored according to the current USPI.

9.5 Compliance

The administration of metreleptin (dose and duration) should be recorded in the appropriate sections of the Case Report Form.

Confidential Page 44 of 58

Information regarding the patient's prescription renewal will be used to support treatment compliance.

9.6 Accountability

Study drug will not be provided.

9.7 Concomitant and Other Treatments

Patients receiving immunomodulatory drugs should not be enrolled in this study (refer to Section 4.4).

9.7.1 Other Concomitant Treatment

Unless excluded (Section 4.4), medication considered necessary for the patient's safety and well-being may be given at the discretion of the Investigator and should recorded in the appropriate sections of the eCRF. Special attention should be paid to recording changes to the patient's anti-diabetic of lipid lowering treatments as these modifications may affect efficacy determination.

10. STATISTICAL ANALYSES

10.1 Statistical Considerations

Analyses will be performed by Aegerion or designee.

A comprehensive Statistical Analysis Plan will be prepared and finalized before database lock.

10.2 Sample Size Estimate

Ten patients who have been prescribed metreleptin for generalized lipodystrophy will be included in this study; patients will be evaluated for a period of 3 years.

Pooled data from 2 previous studies of metreleptin for lipodystrophy (NIH 991265/20010769 and FHA101 [NCT00677313, FHA101]) indicated the proportion of patients who developed binding antibodies to metreleptin at titers ≥25 was 80% after treatment with metreleptin. If 10 patients are enrolled in this study, there is 87.9%

Confidential Page 45 of 58

certainty that a minimum of 6 out of the 10 patients will have a titer of binding antibody ≥25. The expected distribution of maximum titer for these 10 patients is presented in 5.

Table 5: Expected Number of Patients with Maximum Antibody Titer

MAXIMUM TITER	NUMBER OF PATIENTS
0	1
5	1
25	1
125	2
625	3
3125	2
15625	0

Studying 10 patients in this rare population is adequate to confirm previous immunogenicity results from both the obesity and lipodystrophy development programs. Following patients for 3 years should be adequate to assess time to peak titer since previous data suggest a range of 4 to 7 months. *In vitro* neutralizing activity will also be measured in all antibody positive samples, and may be detected by either the receptor cell-based assay or the ligand-binding assay (under development). However, if 0 out of 10 enrolled patients is observed with *in vitro* neutralizing activity, the point estimate (90% confidence interval) for the proportion of patients with neutralizing activity is 0.00 (0.00, 0.26) (computed in StatXact version 7.0). Because generalized lipodystrophy is a rare disease and events of *in vitro* neutralizing activity are infrequent, it is not feasible to gain a precise estimate of *in vitro* neutralizing activity; this study is not designed to determine this estimate

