10.5 Methods for Statistical Analyses

There will be no hypothesis testing. All data will be summarized by descriptive statistics and/or listings. In general, continuous variables will be summarized by n, mean, SD, median, min and max. Number of patients and percentage of patients in a category will be provided.

Descriptive statistics will be provided for immunogenicity variables (Section 10.4). The maximum antibody titer (anti-metreleptin or anti-HuL) during a visit will be summarized by visit. Categorization of *in vitro* neutralizing activity as assessed by cell-based assay will be summarized across visits; the rate of Category D and E *in vitro* neutralizing activity with 90% and 80% exact confidence intervals will be computed. The results are reported as percent inhibition and 80% inhibition is currently utilized as the neutralizing antibody threshold. activity Results for *in vitro* neutralizing activity will be summarized across visits; however, there will be no formal comparison of the 2 assay methods for the detection and relative potency of Category D or E *in vitro* neutralizing activity.

Maximum antibody titers, neutralizing activities detected by both methods, and metreleptin exposure for each patient will be plotted over time. Maximum antibody

Confidential Page 47 of 58

titers, neutralizing activities detected by both methods, and any associated clinical events (i.e., loss of efficacy or AE) will be summarized.

All AEs will be coded using the Medical Dictionary for Regulatory Activities (MedDRA). The number and percentage of patients who experienced at least 1 AE will be summarized by system organ class and preferred term. AEs will be summarized by relationship to the study medication and by severity. Deaths, SAEs, AESIs, and AEs leading to discontinuation will be tabulated and/or listed. SAEs, AESIs and AEs leading to discontinuation will be summarized respectively by peak antibody titers (antimetreleptin, anti-HuL) and by *in vitro* neutralizing activity categories or percent inhibition.

Clinical laboratory results (hematology, chemistry, and urinalysis), and vital signs results will be summarized using descriptive statistics for each visit.

Change from baseline in HbA1c and percent change from baseline in fasting triglycerides will be summarized for each visit by overall patient population, by peak antibody titers (anti-metreleptin, anti HuL), and by *in vitro* neutralizing activity categories or percent inhibition , respectively.

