#### 4. STUDY DESIGN

### 4.1 General Description

This study is an open-label, Phase 4 trial to provide an assessment of the immunogenicity associated with metreleptin and of any major potential risks due to development of antibodies to metreleptin. The study is being conducted to comply with an Food and Drug Administration post-marketing requirement.

Patients who have been prescribed metreleptin for generalized lipodystrophy, who meet all enrollment criteria and who have signed informed consent for this study at Screening (Visit 1) will receive the first dose of metreleptin at Enrollment/Baseline (Visit 2) at the study site. Patients will return to the study site for follow-up and collection of blood samples at regular intervals (at Month 1, 2, 4, 6, 9, 12, 18, 24, 30, and 36), for a total of 12 visits over approximately 3 years (36 months). Eleven patients who have been prescribed metreleptin will be enrolled.

All patients, including those with suspected loss of metreleptin efficacy (worsening of metabolic control) or endogenous leptin action (serious or severe infections or sepsis) should be tested for *in vitro* neutralizing activity.

The study flow diagram is presented in **Figure 1**.

Patients who sign informed consent and meet all inclusion/exclusion criteria will be enrolled in the study. Assessments will be made at the times specified in the Study Plan (**Table 1** of protocol). At the end of the 3-year study period, patients who still have *in vitro* neutralizing activity should enroll in the separate Immunogenicity Follow-up Program for continued immunogenicity monitoring.

[figure not shown]
Document: Statistical Analysis Plan: AEGR-734-401: A 36-Month, Multicenter, Open Label Phase 4 Study to Evaluate the

Immunogenicity of Daily SC Metreleptin Treatment in Patients with Generalized Lipodystrophy

Author: [name], [name], [name], [name] Version Number: 2.1

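### Protocol 10.2 gives 87.9% as the chance that at least 6 of 10 patients reach titer ≥25; that is the figure for at least 7, and at least 6 is 96.7%

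*Protocol*

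**What the plan says.** Protocol 10.2 (Sample Size Estimate) bases its calculation on pooled data from two earlier lipodystrophy studies, which "indicated the proportion of patients who developed binding antibodies to metreleptin at titers ≥25 was 80% after treatment with metreleptin". It continues: "If 10 patients are enrolled in this study, there is 87.9"% "certainty that a minimum of 6 out of the 10 patients will have a titer of binding antibody ≥25". Table 5 in the same section then sets out the expected distribution of maximum titer in the 10 patients.

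No dropout allowance, interval or significance level is attached to the 87.9%. Protocol 10.5 states: "There will be no hypothesis testing". The figure is therefore a plain probability statement with three inputs: the number of patients, the rate and the threshold count.

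The SAP text available for review neither repeats nor corrects the figure, and SAP 4.3 reports no changes to the analysis from the protocol. SAP 4.1 gives a different enrolment: "Eleven patients who have been prescribed metreleptin will be enrolled".

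**The concern.** All three inputs are printed beside the result, so it can be checked directly. At a true rate of 80% the expected count is 8 of 10, and a result below 6 should be rare. A 12.1% chance of falling short (100 − 87.9) looks too high for a threshold two below the expected count.

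What is at stake is the accuracy of the record. This is the only probability given to support the sample size of a study run to meet a postmarketing requirement. If it does not follow from its own inputs, it could be carried uncorrected into the study report, and a reader who checks it may doubt the neighbouring figures.

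**Working it through.** **Inputs**, all from protocol 10.2: n = 10; p = 0.80 for titer ≥25; threshold at least 6.

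**Formula.** With X ~ Binomial(10, 0.80),

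P(X = k) = C(10, k) × 0.8^k × 0.2^(10−k), and P(X ≥ r) is the sum from k = r to 10.

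**Terms.**

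| k | C(10, k) × 0.8^k × 0.2^(10−k) | P(X = k) | P(X ≥ k) |
|---|---|---|---|
| 10 | 1 × 0.10737 × 1 | 0.1074 | 0.1074 |
| 9 | 10 × 0.13422 × 0.2 | 0.2684 | 0.3758 |
| 8 | 45 × 0.16777 × 0.04 | 0.3020 | 0.6778 |
| 7 | 120 × 0.20972 × 0.008 | 0.2013 | **0.8791** |
| 6 | 210 × 0.26214 × 0.0016 | 0.0881 | **0.9672** |

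**Reproducing the plan's figure.** The stated 87.9% matches P(X ≥ 7) = 0.8791 to the printed decimal. It does not match P(X ≥ 6) = 0.9672. The difference, 0.9672 − 0.8791 = 0.0881, is the single term P(X = 6).

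**Could another reading give 87.9% for at least 6?**

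- Rounding of the rate: p = 0.795 gives 0.9638 and p = 0.805 gives 0.9704.
- A different rate: solving P(X ≥ 6) = 0.879 with n = 10 gives p = 0.718. Table 5 contradicts this, because its entries at titers 25, 125, 625 and 3125 sum to 1 + 2 + 3 + 2 = 8 of 10, which is 80%.
- A different n at p = 0.80: n = 9 gives 0.9144 and n = 11 gives 0.988.
- A normal approximation (mean 8, variance 10 × 0.8 × 0.2 = 1.6): 0.976 with continuity correction and 0.943 without.

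None of these gives 87.9%.

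**The other figure in the section.** For 0 of 10, the upper limit of the exact two-sided 90% interval is 1 − 0.05^(1/10) = 0.259, which rounds to the protocol's 0.26. That figure is correct.

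**If 11 patients were used instead** (SAP 4.1), still at p = 0.80: at least 6 is 98.8%, at least 7 is 95.0% and at least 8 is 83.9%. The upper limit for 0 of 11 is 1 − 0.05^(1/11) = 0.238.

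**The case against.** The best argument on the other side concerns weight. The figure drives nothing: there is no hypothesis test, success threshold or decision rule, and the protocol itself points to the rarity of the disease. The error understates the chance of at least 6, so it does not flatter the design. The SAP does not repeat the number, so its passage into the study report is a possibility and not a certainty. The change record attached to the SAP includes changes made after database lock (dated 26 February 2025), so a protocol amendment would now achieve little. All of this stands and is why the point is minor.

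Two further cautions also stand. First, the documents give no method for the 87.9%. More than 6 may have been computed and labelled as at least 6, or a 6 may have been typed for an intended 7; the text cannot settle which. One can say only that the number matches at least 7. Second, the 11-patient figures are not a correction of 10.2, which speaks of 10 patients. They also assume that the 80% rate at titer ≥25 carries over, whereas SAP 15.2 reports titers on a different scale (1:10, 1:50, 1:250 and so on).

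None of this rescues the statement as written: 10 patients, 80% and at least 6 do not give 87.9%.

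**Conclusion.** The concern holds. On the protocol's own inputs, the probability that at least 6 of 10 patients reach a titer of 25 or more is 96.7%, not 87.9%. The printed figure is 8.8 percentage points too low for its label and is correct for at least 7 of 10.

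The result rests on independent patients with a common true rate of 80%, which is the simplest reading of 10.2 and the one that reproduces 87.9% at the neighbouring count. Severity is minor: 10 patients, Table 5, the 0-of-10 interval and every planned analysis remain as they are.

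**What to change.** Change either the count or the percentage in protocol 10.2, so that it reads at least 7 of 10 with 87.9%, or at least 6 of 10 with 96.7%. The sponsor should choose according to which threshold was meant. As the database is already locked, one correcting sentence in the study report, where the sample-size rationale is described, would do equally well.

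If the report restates the rationale for the 11 patients in SAP 4.1, it should use the 11-patient figures above and say that they keep the 80% rate and the protocol's titer scale.

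The cost is one number or one word in the protocol, or one sentence in the report. No sample-size change, new analysis or programming is needed.
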